## 4.0 PARTICIPANT ENTRY

### 4.1 PRE-REGISTRATION EVALUATIONS

All participants of the study will undergo routine pre-operative assessment including tests for Methicillin-resistant Staphylococcus aureus (MRSA) and COVID-19 and a full blood count. Given the indication for referral to the gynaecology clinic, all participants of the study will have an ultrasound scan to assess the nature and size of their ovarian cyst.

### 4.2 INCLUSION CRITERIA

All females of reproductive age with a diagnosis of a benign ovarian cyst requiring surgical management.

This includes cysts defined as dermoid, teratoma, simple cyst, functional, serous cystadenoma or mucinous cystadenoma from the initial diagnostic ultrasound.

A strict criterion for the US diagnostic features will include the following:

- Cyst size  $\geq 3\text{cm}$ ;  $\leq 10\text{cm}$
- International Ovarian Tumour Analysis Benign features (IOTA B):
  - Unilocular
  - Solid components: largest diameter  $\leq 7\text{mm}$
  - Acoustic shadows
  - No blood flow
  - Smooth multilocular cyst: largest diameter  $\leq 10\text{cm}$

Specifically:

- Pregnant participants can be included but will be analysed separately
- For participants selected for surgery, delay of surgery is not an exclusion criterion for this study, but for selected objectives we will use only those participants in whom surgery was performed within 180 days after the ultrasound examination
- With regards to age, participants can be selected only if 18-50 years old
- Participants whom only underwent transabdominal scanning can be included in the study, but will be analysed separately

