## 3.0 STUDY DESIGN

This will be a multi-centre prospective cohort study carried out as a non-blinded randomised controlled trial. Participants will be allocated to either a control group of laparoscopic ovarian cystectomy performed without ultrasound guidance, or to the experimental ultrasound guided laparoscopic ovarian cystectomy (UGLOC) group. All surgeons operating and participants recruited to the study will be aware of which group they have been allocated to from the beginning of the study. The investigators aim for equal sample sizes in both groups (see power calculation below).

Participants will include all women of reproductive age diagnosed with a benign ovarian cyst requiring surgical management. The duration of the study from recruitment to end of data collection will be approximately 3 years (01/10/21-01/10/24).

Women referred to the outpatient gynecology clinic with a suspected ovarian cyst will be asked about their clinical history and undergo a pelvic transvaginal ultrasound scan (2D and 3D ultrasonography) as part of routine clinical care. If an ovarian cyst is seen on ultrasound, it will be assessed according to local protocols based on simple descriptors and international ovarian tumor analysis (IOTA) simple rules. Depending on the severity of symptoms, nature of the cyst and fulfilment of the inclusion criteria and if the woman is suitable for surgical management, she will then be invited to participate in the study.

Participants will be recruited from various general gynaecology clinics as well as specialist clinics including: ovarian cyst, the IOTA and rapid access clinics across Imperial and University College London Hospital.

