### *Data Collection*

The investigators will collect the following data: patient demographics including age, BMI, gravida, parity and gynaecological surgical history. Pre-operative data will include findings from the diagnostic transvaginal scan and measure of ovarian reserve: AMH and AFC. Intra-operative data will include transvaginal findings during surgery (in the experimental group only), such as cyst location and size or any new lesions noted. Residual ovarian volume post cystectomy will also be measured intraoperatively. Histology data will include the histological diagnosis of the ovarian cyst and volume of normal ovarian tissue excised during the cystectomy measured as per margins in mm. Outcomes following surgery including duration of surgery (mins), length of hospital stay (days) and post op complications will be recorded.

Post operatively, participants will return to clinic for follow up at 3 and 6 months post -surgery, whereby a blood test will be taken to assess ovarian reserve by measuring the AMH level. The outpatient gynaecology nurse in clinic or research staff will be responsible for taking the blood sample

and will only require one EDTA bottle (yellow top) to be filled (20-40mls). The blood samples will be processed by Imperial College Healthcare Trust laboratories or University College London Hospitals NHS Foundation Trust, depending on the site taken, and will be discarded as per local protocol once the AMH has been determined. There are no specific storage or transfer requirements outside of normal practice. Therefore, samples will be ‘podded’ to the labs once taken in the usual way. In addition, an ultrasound will be performed during the follow up appointment to measure AFC and assess volume of preserved ovarian tissue. Follow up appointments should take approximately 20 minutes. The two blood tests and two ultrasound scans carried out during the follow up process are considered standard clinical practice, and therefore not considered additional investigations for the purpose of this research study.

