### 3.1 STUDY OUTCOME MEASURES

Primary: AMH and AFC measurements at 3 and 6 months post-surgery.

Secondary: Surgical outcomes including:

- Duration of surgical procedure (minutes),
- Duration of hospital stay (days)
- Presence of intra-operative cyst rupture or spillage (Yes/No)

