**Please send SAE forms to: [[contact]](mailto:[contact])**

**[contact] (Mon to Fri 09.00 – 17.00)**

## 6.0 ASSESSMENT AND FOLLOW-UP

Follow up appointments at 3 and 6 months post -surgery will be carried out at the participants' respective hospital gynecology clinic responsible for the care and management of the ovarian cyst. During this appointment, the responsible physician will assess recovery post- surgery and perform a clinical assessment. A blood test to measure ovarian reserve including assessment of AMH will be taken by the outpatient gynaecology nurse or research staff assigned to the clinic. A transvaginal ultrasound scan will be performed during the appointment by an experienced gynaecology specialist trainee or Consultant to assess the AFC and preserved ovarian volume of tissue remaining. Any incidental findings identified on ultrasound scan of gynaecological pathology, will be managed by the responsible clinician and the participants GP will be informed by letter.

The majority of participants are likely to be discharged following the 2nd clinic appointment 6 months post- surgery, whereby no further involvement is required in the study. If a participant becomes pregnant during the follow up period, follow up will be deferred to 3 and 6 months post completion of pregnancy.

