**(Table 1)**

Figure 1: Normed percentile transformation of AMH Values

[figure not shown]

Table 1: Estimated values of AMH differences based on normed percentile transformation

AMH Differences (pmol/L)		
	Treatment Group	Control Group
Mean	17.06	3.57
Standard Deviation (SD)	22.28	4.31
Coefficient of variation (CV) =(SD/Mean)	1.31	1.21
Number of participants	5	100

Using the pilot data, the investigators anticipate that 32 participants will be required to demonstrate a differential AMH level. (**Table 2**)

Table 2: Power Calculation

Sample Size Calculation		
	Treatment Group	Control Group
Mean (pilot)	17.06	3.57
Standard Deviation SD (pilot)	22.28	4.31
Standard Error (S.E)	6.18	1.08
Lower CI	4.70	1.42
Upper CI	29.42	5.73
Minimum (n)	11	11
Small sample margin	2	2
Attrition (assumed)	3	3
Total (n)	16	16

The minimum sample size is 11 participants. Considering the small size of the pilot and the very low risks thus far, the investigators include 2 more observations to boost power, and assume an attrition rate of approximately 25%. This leads to a total (n) of 16 participants per arm, with a power of 0.95 to detect a difference at the 5% level using a standard t-test on the log-transformed difference in means of AMH, the robust proxy for fertility. It will be necessary to perform an interim analysis given the low number of participants available for the power calculation.

With regards to further data analysis of the study, the investigators plan to use descriptive statistics (mean +/- standard deviation), two-sided tests, and Wilcoxon rank sum test to compare continuous variables in two groups. For more than two groups, the Kruskal-Wallis exact test will be used. For comparing a proportion with an expected value, a binomial exact test will be used. Results are considered significant at  $p<0.05$ . Analysis will be performed with SAS (version 9.2) and Statistical Package for Social Sciences for Windows (version 16). Statistical analysis will be performed under the supervision of [name].

Data and all appropriate documentation will be stored for a minimum of 10 years after the completion of the study, including the follow-up period.

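### Section 4.2 sets randomised women with only a transabdominal scan apart from the main analysis, although their AMH results are valid and the sample size makes no allowance for losing them

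*SAP*

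**What the plan says.** The eligibility rule, SAP section 4.2: "Participants whom only underwent transabdominal scanning can be included in the study, but will be analysed separately". The SAP does not say what the separate analysis is, what the main analysis set is, or which scan puts a woman in this category.

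The outcomes, section 3.1: "Primary: AMH and AFC measurements at 3 and 6 months post-surgery". AMH comes from blood (section 3.0, Data Collection): "a blood test will be taken to assess ovarian reserve by measuring the AMH level". AFC at follow-up comes from a scan (section 6.0): "A transvaginal ultrasound scan will be performed during the appointment by an experienced gynaecology specialist trainee or Consultant to assess the AFC".

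Scan route elsewhere:
- Section 3.0 says that women referred with a suspected cyst "undergo a pelvic transvaginal ultrasound scan (2D and 3D ultrasonography) as part of routine clinical care".
- Section 3.0, Data Collection, on the UGLOC arm: "Intra-operative data will include transvaginal findings during surgery (in the experimental group only".
- Appendix 1 lists transvaginal ultrasound before treatment and at months 3 and 6, and no other kind of scan.
- Section 4.1 asks for an ultrasound scan without naming a route.

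Sample size, section 7.0 and Table 2: a minimum of 11 per arm, plus 2 as a small-sample margin, plus 3 for attrition, making 16 per arm and 32 in total, "with a power of 0.95 to detect a difference at the 5% level" and "using a standard t-test on the log-transformed difference in means of AMH".

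**The concern.** A woman is randomised, has her operation and gives blood at 3 and 6 months. Her AMH is as valid as anyone else's, whatever scan she had at diagnosis. Setting her apart for scan route discards information on the one variable that drives the sample size. It also sits oddly beside section 4.4, which keeps women who received a different treatment from the one specified in both follow-up and analysis.

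Two things are at stake. The first is precision: in a trial of 32 every woman counts, and a separate analysis of a handful would tell little. The second is that the category is undefined. If it means the diagnostic scan, it is fixed before allocation and cannot differ by arm except by chance. If a scan at surgery could change it, the intra-operative transvaginal scan, recorded in the UGLOC arm only, could move women out of the category in that arm and not in the other.

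**Working it through.** **Inputs** (SAP Tables 1 and 2). UGLOC mean 17.06, SD 22.28; control mean 3.57, SD 4.31 (pmol/L). Equal arms, 5% level, power 0.95. Two-sided testing is stated for the further analyses and assumed here for the power calculation. Attrition is about 25% in the text of section 7.0, but 3/16 = 18.75% in Table 2, so both are used. The share scanned only transabdominally is not given; 5%, 10% and 20% are assumptions.

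**Step 1. Reproduce the plan's figure.** For a log-normal variable:
- log-SD = √ln(1 + (SD/mean)²): 0.998 for UGLOC, 0.948 for control, pooled √((0.998² + 0.948²)/2) = 0.973.
- log-mean = ln(mean) − log-SD²/2: 2.339 for UGLOC, 0.823 for control, difference 1.516.
- n per arm = 2(1.960 + 1.645)² × 0.973²/1.516² = 10.7, rounded up to **11**.

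This matches the minimum of 11 in Table 2. At 11 per arm the normal-approximation power is 0.955. The exact (noncentral t) power of the t-test is 0.935, so 11 is already slightly short of 0.95 for the test named.

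**Step 2. What the 16 covers.** 16 = 11 + 2 + 3. The 2 is a margin for the small pilot and the 3 is attrition. No term covers women analysed separately.

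**Step 3. Women left in the main AMH comparison.** Evaluable per arm = 16 × (1 − share set aside) × (1 − attrition), rounded down, with exact t-test power at difference 1.516 and SD 0.973.

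| Share set aside (assumed) | 18.75% attrition: n per arm (power) | 25% attrition: n per arm (power) |
|---|---|---|
| 0% | 13 (0.968) | 12 (0.954) |
| 5% | 12.35 → 12 (0.954) | 11.4 → 11 (0.935) |
| 10% | 11.7 → 11 (0.935) | 10.8 → 10 (0.909) |
| 20% | 10.4 → 10 (0.909) | 9.6 → 9 (0.873) |

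In women, 5%, 10% and 20% of 32 are 1.6, 3.2 and 6.4. With nobody set aside, exact power stays above 0.95 at either attrition rate. At the 25% named in the text, even a 5% share takes it below.

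**Step 4. Scan route, side by side.** Section 3.0 has referred women scanned transvaginally as routine, while section 4.2 provides for women who were not. Section 6.0 and Appendix 1 give only a transvaginal scan at follow-up, and Data Collection describes the intra-operative findings only as transvaginal. No non-transvaginal route for AFC or for the UGLOC findings is described anywhere, so these sections do not fit together for the women whom section 4.2 admits.

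**The case against.** The strongest case on the other side has four parts.

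- **The share may be close to nil.** Section 3.0 makes the transvaginal scan routine, so the rule may never bite. This stands. It is why the power figures are conditional and why no single loss can be stated.
- **The loss is small.** Even at an assumed 20%, power remains 0.87–0.91. This also stands, but only because the assumed effect is very large and its UGLOC side comes from a pilot of five women.
- **There is no bias.** If the category is the diagnostic scan, it precedes randomisation and separating these women costs precision only. This stands on that condition, which the bullet does not state.
- **Separate handling is sensible for AFC.** A baseline AFC not taken transvaginally may not be comparable with the rest. That is fair, but it justifies setting aside one baseline value. It does not justify setting aside the woman's AMH or a follow-up AFC taken transvaginally.

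A reader might go further and infer that some of these women cannot receive UGLOC or have AFC measured, so that the UGLOC arm would include women who had in effect the control operation. The SAP does not support this. The bullet is in the past tense and most naturally describes a scan already done. Section 6.0 and Appendix 1 schedule transvaginal follow-up scans without exception. The sections that define the intervention say only that it is ultrasound guided. The transvaginal wording comes from a data-collection sentence, and nothing states that the technique requires that route. For the same reason the documents give no ground for a new eligibility requirement on transvaginal scanning.

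**Conclusion.** The point holds as a modest but real fault in a stated rule. Followed as written, section 4.2 removes valid randomised AMH results from the main comparison of a 32-woman trial, for a reason that has no bearing on AMH and with no allowance in the sample size.

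The size depends on a share that the SAP does not give. It runs from no loss, if no such woman enters, to exact power of about 0.87–0.91 at an assumed 20%. These figures rest on the plan's own means and SDs, log-normality, two-sided testing, equal loss in both arms and attrition of 18.75–25%. The harm is lost precision. Differential reclassification between arms is a possibility left open by the undefined category, not something the SAP prescribes.

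**What to change.** In section 4.2:

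1. Delete the separate-analysis clause for women scanned only transabdominally.
2. Define the category by the diagnostic scan done before randomisation, so that no later scan can change it.
3. State that these women stay in the main analysis of AMH and in the analysis of follow-up AFC, and that only a baseline AFC not taken transvaginally is treated as missing.
4. If wished, add a sensitivity analysis that leaves them out.

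Separately, reconcile sections 3.0 (including Data Collection), 4.2 and 6.0 and Appendix 1 on scan route, so that the plan says how AFC and the UGLOC findings are obtained for every woman it admits.

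The cost is the rewording of one bullet and a consistency check. The downside is a few missing baseline AFC values. Neither eligibility nor sample size needs to change for this point.

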### 4.3 EXCLUSION CRITERIA

- Cysts that are deemed to be clearly physiological and less than  $<3\text{ cm}$  in maximum diameter are not eligible for inclusion
- Cysts  $\geq 11\text{cm}$  in maximum diameter
- Non-adnexal masses e.g. peritoneal inclusion cysts (where diagnosis is certain)
- Any cyst with features of malignancy
- The denial or withdrawal of written informed consent
- Females of post- menopausal or peri-menopausal status

### 4.4 WITHDRAWAL CRITERIA

All participants will be consented prior to enrolment, and will receive a full explanatory participant information leaflet. Signed participant consent will be obtained. The right of the participant to refuse to partake in the trial without giving reasons will be respected. After the participant has entered the study the clinician remains free to give alternative treatment to that specified in the protocol at any stage if it is in the participant's best interest, but the reasons for doing so should be recorded. In these

cases, the participants remain within the study for the purposes of follow-up and data analysis. All participants are free to withdraw at any time from the protocol treatment without giving reasons and without prejudicing further treatment. All data captured in relation to their participation may be destroyed at their request.

## 5.0 ADVERSE EVENTS

### 5.1 DEFINITIONS

**Adverse Event (AE):** any untoward medical occurrence in a patient or clinical study subject.

**Serious Adverse Event (SAE):** any untoward and unexpected medical occurrence or effect that:

- **Results in death**
- **Is life-threatening** – *refers to an event in which the subject was at risk of death at the time of the event; it does not refer to an event which hypothetically might have caused death if it were more severe*
- **Requires hospitalisation, or prolongation of existing inpatients' hospitalisation**
- **Results in persistent or significant disability or incapacity**
- **Is a congenital anomaly or birth defect**

Medical judgement should be exercised in deciding whether an AE is serious in other situations.

Important AEs that are not immediately life-threatening or do not result in death or hospitalisation but may jeopardise the subject or may require intervention to prevent one of the other outcomes listed in the definition above, should also be considered serious.

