### 5.2 REPORTING PROCEDURES

All adverse events should be reported. Depending on the nature of the event the reporting procedures below should be followed. Any questions concerning adverse event reporting should be directed to the Chief Investigator in the first instance.

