#### 5.3.2 Serious AEs

An SAE form should be completed and emailed to the chief investigator within 24 hours. However, relapse and death due to other pathology, and hospitalisations for elective treatment of a pre-existing condition do not need reporting as SAEs.

All SAEs should be reported to the Chelsea Research and Ethics Committee where in the opinion of the Chief Investigator, the event was:

- ‘related’, i.e. resulted from the administration of any of the research procedures; and,
- ‘unexpected’, i.e. an event that is not listed in the protocol as an expected occurrence.

Reports of related and unexpected SAEs should be submitted within 15 days of the Chief Investigator becoming aware of the event, using the NRES SAE form for non-IMP studies. The Chief Investigator must also notify the Sponsor of all related and unexpected SAEs.

Local investigators should report any SAEs as required by their Local Research Ethics Committee, Sponsor and/or Research & Development Office.

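### The SAE definition in section 5.1 requires the event to be unexpected, so an expected serious surgical complication, read literally, misses the SAE label and the 24-hour form; the death exemption in 5.3.2 also needs reconciling with 5.1

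*SAP*

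**What the plan says.** Section 5.1 defines an adverse event as "any untoward medical occurrence in a patient or clinical study subject". It sets no condition on expectedness.

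The same section defines a serious adverse event as "any untoward and unexpected medical occurrence or effect that" meets at least one of five criteria. Two matter here: "Results in death" and "Requires hospitalisation, or prolongation of existing inpatients' hospitalisation". Two further clauses widen the category. One states: "Medical judgement should be exercised in deciding whether an AE is serious in other situations". The other brings in important events that fall short of the listed outcomes but put the participant at risk or may need intervention to prevent one of them.

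Section 5.2 states: "All adverse events should be reported". Section 5.3.1 has non-serious events recorded irrespective of expectedness.

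Section 5.3.2 requires an SAE form to reach the Chief Investigator within 24 hours. It exempts certain events from SAE reporting, among them "relapse and death due to other pathology". It then sends to the ethics committee those SAEs that are both related and unexpected, and explains unexpected as "an event that is not listed in the protocol as an expected occurrence". The sponsor is notified of the same subset.

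**The concern.** Seriousness and expectedness are different properties of an event, and sections 5.1 and 5.3.2 treat them differently. Section 5.1 makes expectedness part of what an SAE is. Section 5.3.2 makes it a filter applied to events that are already SAEs. Both cannot be operative.

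The discrepancy matters because the trial compares two surgical techniques. Many recognised serious complications of laparoscopic surgery would be regarded as expected. If a site follows the definition to the letter, those events fall outside the SAE category and outside its only stated time limit for reaching the Chief Investigator. Another site that takes its cue from 5.3.2 would submit a form for the same event. Surgery takes place at two Trusts (section 3.0, Surgical Intervention), so two sites could classify like events differently while each follows the text.

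A second inconsistency stands apart from the first. Death is a defining criterion in 5.1 with no exception attached, yet 5.3.2 removes some deaths from SAE reporting.

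**Working it through.** No arithmetic applies. The SAP states no figure on this point and gives no complication or SAE rate, so the check is to set the sections side by side and trace events through them.

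**Step 1: is the second expectedness test redundant?** Under 5.1, every SAE is unexpected. Under 5.3.2, SAEs are divided into expected and unexpected, and only those that are unexpected as well as related go onward. If 5.1 holds as written, the expected group is empty and the test in 5.3.2 excludes nothing. If the test in 5.3.2 has a purpose, expected SAEs exist and 5.1 is wrong as written.

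**Step 2: an expected complication that prolongs the hospital stay.**

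| Section | Question | Result on the literal text |
|---|---|---|
| 5.1, AE definition | Is it an adverse event? | Yes; expectedness is irrelevant |
| 5.1, SAE criteria | Does it meet a seriousness criterion? | Yes, hospitalisation |
| 5.1, SAE definition | Is it an SAE? | No, because it is expected |
| 5.3.2 | Is the 24-hour form triggered? | No, the form is for SAEs |
| 5.2 and 5.3.1 | Is it reported or recorded? | Yes, as an adverse event |
| 3.0, Data Collection | Is it recorded elsewhere? | Yes, as a post-operative complication, with length of stay |

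**Step 3: do the widening clauses in 5.1 repair this?** The medical-judgement clause is for situations other than those listed, and hospitalisation is listed. The important-event clause is aimed at events that stop short of outcomes such as death or hospitalisation, and it carries no expectedness condition. Read literally, an expected lesser event that may endanger the participant counts as serious, while an expected event that actually prolongs her stay does not. Neither clause closes the gap.

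**Step 4: deaths.** Under 5.1, an unexpected death is an SAE whatever its cause. Under 5.3.2, a death attributed to other pathology needs no SAE report. The text shown does not define other pathology or say who makes the attribution. A death caused by the operation is not due to other pathology on a natural reading, so it is not exempt.

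**The case against.** The strongest case on the other side is that little follows in practice. Section 5.3.2 plainly assumes that expected SAEs exist, and the important-event clause in 5.1 has no expectedness condition, so a sensible reader would treat the extra word in 5.1 as a slip. That is fair as a guess at what was intended. It does not tell a site which section to follow, and the literal definition is the one a form-filler would consult.

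A reader might infer that serious surgical complications would go wholly uncounted. The document does not support that: sections 3.0, 5.2 and 5.3.1 between them keep these events in the record. What is lost is the SAE label and the 24-hour route.

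A reader might also infer that the death exemption hides surgical deaths. It does not, since it is limited to other pathology. It can further be said that a general definition followed by a stated exemption is simply a rule with an exception, and that exempt deaths remain reportable adverse events under 5.2. That weakens the point about deaths to one of consistency, but 5.1 gives no sign that an exception follows.

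Finally, no comparison of SAEs by arm is planned. The outcomes in section 3.1 are AMH, AFC, duration of surgery, hospital stay and cyst rupture or spillage, and section 7.0 specifies no SAE analysis. This objection stands: no stated analysis is altered.

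**Conclusion.** The point holds as an inconsistency in the safety-reporting rules. As written, section 5.1 excludes expected serious events from the SAE category, and 5.3.2 presupposes that they belong to it. The effect is on which events reach the Chief Investigator within 24 hours and on any tally of SAEs, not on whether events are recorded at all and not on the primary or secondary analyses. The death exemption is a separate and smaller inconsistency.

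The size cannot be calculated, because the document gives no rate of expected serious complications. The conclusion rests on a literal reading of 5.1 and on the assumption that at least some serious surgical complications would be regarded as expected. It does not rest on there being no list of expected occurrences: none appears in the text at hand, but some text after 5.3.2 was not available, so no point is made of it.

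**What to change.** In section 5.1, delete the expectedness condition from the SAE definition, so that the seriousness criteria alone decide whether an event is an SAE. In section 5.3.2, keep relatedness and expectedness as they stand, solely as the two tests for onward reporting to the ethics committee and the sponsor. The 24-hour form then applies to serious events whether or not they are expected, subject to the exemptions that 5.3.2 states.

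Separately, reconcile the unqualified death criterion in 5.1 with the exemption in 5.3.2, so that both sections give the same answer for a death attributed to other pathology.

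The cost is a wording change in two sections and a few more SAE forms. No outcome, sample size or analysis changes.
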